# PROTOCOL

“Continuous ovarian stimulation in DUOSTIM cycles”

Date: May 7, 2022

---

Despite its growing popularity, ovarian stimulation over prolonged periods involves the application of a large number of injectable medications, resulting in an increased therapeutic burden for the patient. Therefore, there is a need for research into simplified protocols to guarantee optimal patient outcomes not affecting the DuoStim treatment efficiency. At present, we have the physiological basis and optimal drugs to achieve this objective.

## 1. Objectives

The present study aims to explore the progesterone and Corifolitropin alpha application in DuoStim cycles, following the follicular surges concept, in order to alleviate treatment burden in patients indicated for DuoStim cycles and without diminishing the technique's efficacy or safety. Could continuous weekly dosing constitute a viable alternative to daily FSH administration, to obtain a comparable oocyte yield?

## 2. Materials and methods

### 2.1. Study design and Patients

From November 2022 to May 2023, an observational cohort study was conducted at Instituto Bernabeu Alicante to assess non-inferiority. All procedures were performed in a single laboratory and the study was registered (NCT05815719) and validated by the Instituto Bernabeu review committee (IBMR31/01-06-2022). All subjects provided informed consent prior to participation.

The cohort included patients under the DuoStim protocol at the beginning of the stimulation process. Patients with ovarian pathology (e.g., cysts or tumours, with the exception of endometriomas <4 cm) at the time of stimulation initiation were not included.

Baseline determination included age, AMH levels and body mass index (BMI) measurements.

### 2.2. Procedures

On the one hand, the study group (**n=15**) received subcutaneous injections of 150 µg Corifolitropin alpha (Elonva®) consecutively for eight days, together with oral administration of micronized natural progesterone 200 mg/day (to prevent LH peak) during follicular and luteal phase.

On the other hand, the control group (**n=15**) was formed from historical records of patients undergoing DuoStim over the course of 2021 to 2022, following a standard daily FSH/flexible GnRH antagonist protocol. Controls were matched 1 to 1 for age and AMH values ( $\pm 0.4$  pmol/l).

During follicular phase, the GnRH agonist was administered as trigger, whilst the use of hCG or GnRH agonist in luteal phase was permitted.

### **2.3. Result measurements**

The study's main objective was to study the total number of obtained oocytes and the metaphase II stage oocytes rate (stimulation in follicular phase + luteal phase). Secondary objectives included: total number of required injectable and the duration of ovarian stimulation (total days of follicular and luteal phases):

- Stimulation in follicular phase: from the day of the first injectable administration in follicular phase and up to (inclusive) trigger day.
- Stimulation in luteal phase: starting from the day after the first punctum up to and including trigger day in luteal phase.

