### **2.4. Statistical analysis**

A non-inferiority trial was planned with a minimum sample size of 13 patients per group, based on a tolerated difference of  $\pm 1$ , a standard deviation of 1, a statistical power of 80%, and a type 1 error of 5%.

Data were presented as mean  $\pm$  standard deviation (SD). As our data are not random but come from chosen cases and controls with similar age and AMH levels, the samples would be matched. Therefore, differences were analysed using Student's t-test for paired samples if variables had a normal distribution or, the Wilcoxon sign-rank test if a non-normal distribution was assumed.

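### Non-inferiority is the stated aim and there are two unranked main outcomes, but section 2.4 sizes the study for one unnamed outcome and never compares a result with its margin of ±1

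*Combined protocol and SAP*

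**What the plan says.** Section 2.1 describes an observational cohort study "to assess non-inferiority" and ties that aim to no particular outcome. Section 2.3 states that the "main objective was to study the total number of obtained oocytes and the metaphase II stage oocytes rate", counted over "stimulation in follicular phase + luteal phase". The two outcomes are not ranked, and nothing says whether one or both must succeed. The MII rate is given no denominator.

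Section 2.4 holds the only design inputs. The margin is ±1 and the minimum size is 13 per group; the other inputs are "a standard deviation of 1, a statistical power of 80%, and a type 1 error of 5" per cent. Neither the margin nor the SD has a unit or a named outcome, and the sidedness of the 5% is not given.

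For the analysis, section 2.4 treats the data as paired because they come from "chosen cases and controls with similar age and AMH levels, the samples would be matched", in line with section 2.2 ("Controls were matched 1 to 1 for age and AMH values", 15 per group). Differences go to the "t-test for paired samples if variables had a normal distribution", otherwise to the Wilcoxon signed-rank test. The margin does not appear again: there is no confidence limit, no shifted null hypothesis and no decision rule.

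**The concern.** A non-inferiority conclusion needs a margin on a named outcome and an analysis that rules out a loss as large as that margin. Section 2.4 has a margin but does not say what it measures, and the planned tests do not use it.

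Two things are at stake. First, a test of no difference answers another question. If a non-significant result were read as non-inferiority, a treatment that loses the whole tolerated amount could be accepted, and more readily the noisier the data. Second, a reader who sees two main outcomes and one power statement may take the 80% to cover both. The inputs fit one continuous outcome and do not credibly fit a rate.

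**Working it through.** **Inputs from the documents.** Margin 1, SD 1, power 80%, type 1 error 5%, minimum n 13 per group (section 2.4); 15 matched pairs (section 2.2). Oocyte numbers, MII rates, within-pair correlation and any spread other than SD 1 are not given and are assumed below.

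**1. Reproducing n = 13.** For one continuous outcome in two independent groups, one-sided 5%, no true difference:

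n = 2 × ((1.645 + 0.842) × 1/1)² = 12.4, rounded up to 13.

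Other readings give other figures. Two-sided 5% gives 15.7, so 16. A paired formula with an SD of differences of 1 gives (1.645 + 0.842)² = 6.2, so 7 pairs. The arithmetic is therefore sound, and a single continuous outcome uses all of it.

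**2. Could the inputs describe a rate?**
- On the 0–1 scale, a margin of 1 is the whole range and an SD cannot exceed about 0.5. SD 1 is impossible.
- In percentage points, binomial variation alone gives a patient's rate an SD of 100 × √(p(1−p)/m) for m oocytes. With p = 0.80 and m = 20 this is 8.9 points; with p = 0.70 and m = 5 it is 20.5. An SD of 1 point needs m = p(1−p)/0.01², which is 1,600 oocytes per patient at p = 0.80 and 2,100 at p = 0.70. That is not credible, though not mathematically excluded.
- For a count of MII oocytes the units would fit, but the text says rate.

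**3. The planned paired t-test when the true loss equals the margin, at SD 1.** With within-pair correlation ρ, the SD of the differences is √(2(1−ρ)). The noncentrality is √15 divided by that SD, with 14 df.

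| ρ (assumed) | SD of differences | Noncentrality | Non-significant, two-sided 5% | Non-significant, one-sided 5% |
|---|---|---|---|---|
| 0 | 1.41 | 2.74 | 27.8% | 16.9% |
| 0.3 | 1.18 | 3.27 | 14.0% | 7.2% |
| 0.5 | 1.00 | 3.87 | 5.1% | 2.1% |

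**4. The same test with a wider spread.** Here the counts are assumed to vary as Poisson with control means of 5, 10 and 20 and a true loss of 1.

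| Control mean (assumed) | Uncorrelated, two-sided | Uncorrelated, one-sided | ρ = 0.5, two-sided |
|---|---|---|---|
| 5 | about 78% | about 66% | about 64% |
| 10 | about 87% | about 79% | about 79% |
| 20 | about 91% | about 85% | about 87% |

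The last column is a normal approximation that gives both groups the control SD, so the SD of differences is √(2 × mean × 0.5) = √mean, or 2.24, 3.16 and 4.47. If the study group's variance instead falls with its mean, the figure at mean 5 is about 60% and the other two barely change.

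**5. A rule that uses the margin.** Conclude non-inferiority only if the lower one-sided 95% limit of the mean paired difference exceeds −1. At a true loss of 1 this passes 5% of studies under normality. In simulation with uncorrelated Poisson counts it passed 5.0%, 5.0% and 4.9% at means 5, 10 and 20. With no true loss it succeeds in 83% of studies at SD 1 with uncorrelated pairs, but in only about 32%, 21% and 14% under the Poisson spreads.

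**The case against.** The strongest reply is that section 1 asks only whether the number of oocytes obtained is comparable. On that reading ±1 and SD 1 are oocytes, one calculation on one lead outcome is ordinary practice, and no non-inferiority claim is made for maturity. This largely stands. A reader might infer that the study claims non-inferiority for the MII rate and fails to power it, but section 2.1 names no outcome and section 2.3 speaks only of studying both. What remains is that two unranked main outcomes share one power statement that fits only one of them.

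A second reply is that section 2.4 does not say that a non-significant test means non-inferiority, and that either test could be shifted to the margin. Both points are true. The charge is therefore not that the plan adopts a wrong rule. It states none, and the tests as described do not supply one.

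A third reply is that matching on age and AMH should induce correlation, which lowers the error at SD 1. That also stands. At a correlation of 0.5 the two-sided figure is 5.1%, so the excess can vanish at the plan's own SD. It does not vanish under Poisson-scale spread, but that spread is assumed and not taken from the documents.

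**Conclusion.** The concern holds in a limited form. Section 2.4 followed as written gives no valid non-inferiority conclusion on either main outcome, because no result is compared with ±1 and the outcome that ±1 measures is not named. This rests on the text alone and needs no assumption. The sample size of 13 is not an arithmetic error.

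The size of the risk is conditional. If non-significance were taken as success at a true loss of 1 oocyte with 15 pairs, false acceptance at SD 1 would run from about 28% to 5% (two-sided) or 17% to 2% (one-sided) as the assumed correlation goes from 0 to 0.5. Under assumed Poisson spread it is large in every case computed, about 64% to 91% two-sided. A reader might infer that the error always far exceeds 5%; at the plan's own SD the documents do not support that, since they give neither the correlation nor the sidedness.

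A reader might also infer that the inputs can describe no rate at all. That is strictly so only on the 0–1 scale. In percentage points they are not credible, and for a count of MII oocytes they could fit. Either way, the stated 80% power does not extend to the MII rate as worded.

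**What to change.** In sections 2.3 and 2.4:

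- Name the outcome and unit to which ±1 and SD 1 refer. Define the MII rate with its denominator, and say how a patient with no oocytes is handled.
- For the named outcome (total oocytes over both phases or, if that was meant, the number of MII oocytes), conclude non-inferiority only if the lower one-sided 95% confidence limit of the mean paired difference, study minus control, lies above −1. If the data are judged non-normal, compare the matching signed-rank (Hodges–Lehmann) limit with −1 instead.
- Restrict the 80% power statement to that outcome and to the assumed SD of 1. Report the observed group SDs beside 1, and the observed SD of the paired differences beside the √2 × 1 = 1.41 that the independent-groups calculation implies.
- Report the MII rate as a paired difference with a 95% interval and no non-inferiority claim. No margin was set for it, and one chosen now would come after the study.
- Date the change and disclose it as post hoc, since the text describes a study already conducted.

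The cost is wording and two interval analyses on existing data, with no new patients. Maturity carries no confirmatory claim. If the spread is much wider than SD 1, non-inferiority will probably not be shown even when there is no true loss.

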### **2.4. Statistical analysis**

A non-inferiority trial was planned with a minimum sample size of 13 patients per group, based on a tolerated difference of  $\pm 1$ , a standard deviation of 1, a statistical power of 80%, and a type 1 error of 5%.

Data were presented as mean  $\pm$  standard deviation (SD). As our data are not random but come from chosen cases and controls with similar age and AMH levels, the samples would be matched. Therefore, differences were analysed using Student's t-test for paired samples if variables had a normal distribution or, the Wilcoxon sign-rank test if a non-normal distribution was assumed.

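### The study is planned and sized for non-inferiority with a tolerated difference of ±1, but section 2.4 names only paired tests of differences and never compares a result with that margin

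*Combined protocol and SAP*

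**What the plan says.** Section 2.1 describes "an observational cohort study was conducted at Instituto Bernabeu Alicante to assess non-inferiority". Section 1 gives the aim as easing "treatment burden in patients indicated for DuoStim cycles and without diminishing the" efficacy or safety of the technique, and asks about a comparable oocyte yield. Section 2.4 begins: "A non-inferiority trial was planned with a minimum sample size of 13 patients per group, based on a tolerated difference of" ±1, with "a standard deviation of 1, a statistical power of 80%, and a type 1 error of 5" percent.

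On analysis, section 2.4 says that data are shown as mean and SD. It bases the paired approach on the way controls were chosen: "the samples would be matched. Therefore, differences were analysed using" one of two procedures, depending on the distribution. These are named as a "t-test for paired samples if variables had a normal distribution or, the Wilcoxon sign-rank test if a non-normal distribution was assumed". The ±1 does not appear again.

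Section 2.3 gives the main objective as two outcomes summed over both phases: the number of oocytes obtained and the metaphase II (MII) rate. Section 2.2 gives 15 study patients and 15 historical controls, matched one to one.

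**The concern.** A paired t-test or signed-rank test against zero asks whether the regimens differ. Non-inferiority asks whether a loss beyond the margin can be ruled out. The margin sets the sample size and then drops out of the analysis, so the study's main question has no decision rule. The plan does not say that a non-significant p-value will be read as non-inferiority, but it offers no other route to that conclusion.

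Two features of the margin are also open.

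- **Direction.** ±1 could be a one-sided bound or an equivalence range.
- **Unit and outcome.** None is given. A margin of 1 may be sensible for an oocyte count. For the MII rate it is either the whole range (as a proportion) or one percentage point (as a percentage).

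**Working it through.** **Inputs.** From section 2.4: margin 1, SD 1, power 80%, type 1 error 5%. From section 2.2: 15 pairs. Assumed, because the documents do not give them: true difference 0 for sizing, SD 1 read as the SD per patient, and a pair correlation ρ from 0 to 0.7.

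**1. The plan's sample size** (normal approximation, per group).

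- Non-inferiority, one-sided 5%: 2 × (1.645 + 0.842)² = 12.37, rounded up to 13. This matches the plan.
- Non-inferiority, one-sided 2.5%: 15.70, rounded up to 16.
- Equivalence, 5% on each side: 2 × (1.645 + 1.282)² = 17.13, rounded up to 18.
- Paired, with SD 1 for the differences: (1.645 + 0.842)² = 6.18, rounded up to 7 pairs.

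A one-sided superiority formula with a difference of 1 is algebraically the same as the first line and also gives 13. The number therefore fits a one-sided bound, but it is the plan's own wording that makes it non-inferiority.

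**2. Where the two rules part on the observed scale.** The SD of a within-pair difference is √(2(1 − ρ)). With 14 degrees of freedom, t(0.975) = 2.145 and t(0.95) = 1.761.

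- A two-sided 5% test against zero is non-significant for a mean deficit up to 2.145 × SDdiff/√15.
- The margin is met when the mean difference (study minus control) exceeds −1 + 1.761 × SDdiff/√15.

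| ρ | SDdiff | Non-significant up to a deficit of | Margin met up to a deficit of |
|---|---|---|---|
| 0 | 1.414 | 0.78 | 0.36 |
| 0.3 | 1.183 | 0.66 | 0.46 |
| 0.5 | 1.000 | 0.55 | 0.55 |
| 0.7 | 0.775 | 0.43 | 0.65 |

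At ρ = 0, an observed deficit between 0.36 and 0.78 is non-significant yet does not show non-inferiority. At ρ = 0.7, a deficit between 0.43 and 0.65 is significant yet meets the margin. At ρ = 0.5 the limits almost coincide.

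**3. How often this happens** (400,000 simulated studies, normal differences, SD estimated in each study), at a true deficit of 0.5:

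| ρ | Non-significant, non-inferiority not shown | Significant deficit, margin met | Either |
|---|---|---|---|
| 0 | 39% | 1% | 40% |
| 0.3 | 24% | 3% | 27% |
| 0.5 | 10% | 12% | 22% |
| 0.7 | 1% | 42% | 43% |

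At a true difference of 0 the total is 15% at ρ = 0 and about 3% at ρ = 0.5.

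**4. If non-significance were read as non-inferiority.** At a true deficit of exactly 1, the noncentral t distribution gives a non-significant result with probability 27.8%, 14.0%, 5.1% and 0.4% for ρ = 0, 0.3, 0.5 and 0.7. With an assumed SD of differences of 2 or 3 it would be 56% or 77%.

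**The case against.** The strongest reply is that this is an omission and not a contradiction. No null value is written down, and either test can be run on differences shifted by the margin. That is true, but nothing says that it will be done, and a reader following section 2.4 would test against zero.

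A second reply is that the size of the problem rests on assumed values. The correlation and the deficit of 0.5 are not in the documents, and 0.5 lies midway between zero and the margin. If the SD of 1 belongs to the paired differences (the same as ρ = 0.5), misreading non-significance carries a 5.1% error, which is no real inflation. This stands: the percentages are conditional, and the defect rests on logic, not on any one of them.

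Third, the ± sign and the aim of a comparable yield also fit equivalence. That is fair, and it is why the sponsor must confirm the direction. The declared non-inferiority, the aim of not reducing efficacy and the figure of 13 all favour a one-sided bound.

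Fourth, one percentage point is formally usable as a margin for the MII rate. That too is correct, although it would be very strict and nothing in the plan suggests it was meant. Restricting the formal claim to oocytes is an endpoint decision for the sponsor and more than an edit.

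Finally, the Hodges-Lehmann interval concerns a pseudomedian and not a mean, so the same −1 would apply to a slightly different quantity when the Wilcoxon test is chosen.

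**Conclusion.** The concern holds and must be fixed. The plan's 13 per group reproduces as a one-sided 5% non-inferiority calculation, but the named analysis does not test that hypothesis and no section supplies a rule for concluding it. The mismatch can act in either direction: a non-significant result may leave a loss of more than 1 open, and a significant deficit may still lie within the margin.

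The practical effect depends on values that the documents do not give. It ranges from about 3% of studies with conflicting answers (no true difference, ρ = 0.5) to 43% (true deficit 0.5, ρ = 0.7). These figures assume 15 complete pairs, normal differences and the plan's SD of 1 per patient.

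**What to change.** Add to section 2.4:

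> Non-inferiority in total oocytes (follicular plus luteal phase) is concluded only if the lower one-sided 95% confidence limit for the within-pair difference, study minus control, is above −1. The paired-t interval is used, or the Hodges-Lehmann interval where the Wilcoxon test is selected. A non-significant difference test is not evidence of non-inferiority. The margin of 1 is not applied to the MII rate, which is reported with its confidence interval unless a separate margin is given.

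This keeps the plan's choice between the t-test and Wilcoxon. The sponsor must confirm three inferences: that the unit is oocytes, that the 5% is one-sided, and that ±1 means a non-inferiority bound. If equivalence was meant, both limits of the two-sided 90% interval must lie between −1 and +1.

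**Timing.** The protocol carries "Date: May 7, 2022", which precedes the study period ("From November 2022 to May 2023"), yet it is written in the past tense. The documents do not show whether data had been seen. If they had, the rule must be labelled post hoc.

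**Cost.** The work is new wording and two intervals from the same pairs. The formal claim is limited to total oocytes until the MII rate has its own margin, and the conclusion may be less favourable. Power with 15 pairs, true difference 0 and SD 1:

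| Rule | ρ = 0 | ρ = 0.5 |
|---|---|---|
| Paired-t limit, one-sided 5% | 83% | 98% |
| Hodges-Lehmann limit (exact level 4.73%) | 81% | 97% |
| Paired-t limit, one-sided 2.5% | 72% | 95% |
| Equivalence, two-sided 90% interval | 66% | 96% |

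The Hodges-Lehmann row comes from 40,000 simulated normal samples, so it does not describe the non-normal data for which that interval would be used. All values fall if the SD exceeds 1: with an assumed SD of differences of 2, the first rule has 58% power.
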